5.3.4 Avelumab Discontinuation Criteria

The following ADRs require permanent treatment discontinuation of avelumab:

---**Any Grade 4 AEs require treatment discontinuation with avelumab** except for single laboratory values out of normal range that are unlikely related to study treatment as assessed by the Investigator, do not have any clinical correlate, and resolve within 7 days with adequate medical management

---**Any Grade 3 AEs require treatment discontinuation with avelumab except for any of the following:**

- Transient (≤ 6 hours) Grade 3 flu-like symptoms or fever, which is controlled with medical management
- Transient (≤ 24 hours) Grade 3 fatigue, local reactions, headache, nausea, emesis that resolves to Grade ≤ 1
- Single laboratory values out of normal range (excluding Grade ≥ 3 liver function test increase) that are unlikely related to study treatment according to the Investigator, do not have any clinical correlate, and resolve to Grade ≤ 1 within 7 days with adequate medical management
- Tumor flare phenomenon defined as local pain, irritation, or rash localized at sites of known or suspected tumor
- Change in ECOG PS to ≥ 3 that does not resolve to ≤ 2 within 14 days (infusions should not be given on the following cycle, if the ECOG PS is ≥ 3 on the day of study drug administration)

Any Grade 2 AEs should be managed as follows:

- If a Grade 2 AE resolves to Grade \leq 1 by the last day of the current cycle, treatment may continue.
- If a Grade 2 AE does not resolve to Grade \leq 1 by the last day of the current cycle, infusions should not be given on the following cycle. If at the end of the following cycle the event has not resolved to Grade 1, the subject should permanently discontinue treatment with avelumab AE (except for hormone insufficiencies, that can be managed by replacement therapy; for these hormone insufficiencies, up to 2 subsequent doses may be omitted).
- Upon the second occurrence of the same Grade 2 AE (except for hormone insufficiencies that can be managed by replacement therapy) in the same subject, treatment with avelumab has to be permanently discontinued.
- Infusion-related reactions, hypersensitivity reactions (Grades 1 to 4), and tumor lysis syndrome should be handled according to guidelines provided.
- Any dosing interruption lasting $>$ 8 weeks with the following exceptions:
 - o Dosing interruptions to allow for prolonged steroid tapers to manage drug-related adverse events are allowed. Prior to re-initiating treatment in a subject with a dosing interruption lasting $>$ 8 weeks, the PI must be consulted. Tumor/Leukemia assessments should continue as per protocol even if dosing is interrupted.
 - o Dosing interruptions $>$ 8 weeks that occur for non-drug-related reasons may be allowed if approved by the PI. Prior to re-initiating treatment in a subject with a dosing interruption lasting $>$ 8 weeks, the PI must be consulted. Tumor/Leukemia assessments should continue as per protocol even if dosing is interrupted.
 - o Delays in start of subsequent cycles greater than 8 weeks will be acceptable only for patients who are deriving clinical benefit and after discussion with the PI of potential risk/benefit ratio and documentation of this discussion in the patient's medical record.

5.3.5

Detailed management algorithms for immune-oncology drug-related adverse events (including gastrointestinal, renal, pulmonary, hepatic, endocrine, skin and neurological) are provided in Table 3 below. These general guidelines constitute guidance to the Investigator and may be supplemented by discussions with the PI and IND Office in specific cases.

Since inhibition of PD-L1 stimulates the immune system, immune-related AEs (irAEs) may occur. Treatment of irAEs is mainly dependent upon severity (NCI-CTCAE grade):

Grade 1 to 2: treat symptomatically or with moderate dose steroids, more frequent monitoring

Grade 1 to 2 (persistent): manage similar to high grade AE (Grade 3 to 4)

Grade 3 to 4: treat with high dose corticosteroids

Table 3. Management of Immune-Related Adverse Events

Gastrointestinal irAEs		
Severity of Diarrhea / Colitis (NCI-CTCAE v4.03)	Management	Follow-up
Grade 1 Diarrhea: < 4 stools/day over Baseline Colitis: asymptomatic	Continue avelumab therapy Symptomatic treatment (for example, loperamide)	Close monitoring for worsening symptoms Educate subject to report worsening immediately If worsens: Treat as Grade 2 or 3/4
Grade 2 Diarrhea: 4 to 6 stools per day over Baseline; IV fluids indicated < 24 hours; not interfering with ADL Colitis: abdominal pain; blood in stool	Delay avelumab therapy Symptomatic treatment	If improves to Grade 1: Resume avelumab therapy If persists > 5 to 7 days or recur: 0.5 to 1.0 mg/kg/day methylprednisolone or equivalent When symptoms improve to Grade 1, taper steroids over at least 1 month, consider prophylactic antibiotics for opportunistic infections, and resume avelumab therapy per protocol. If worsens or persists > 3 to 5 days with oral steroids: Treat as Grade 3 to 4
Grade 3 to 4 Diarrhea (Grade 3): ≥ 7 stools per day over Baseline; incontinence; IV fluids ≥ 24 hrs; interfering with ADL Colitis (Grade 3): severe abdominal pain, medical intervention indicated, peritoneal signs Grade 4: life-threatening, perforation	Discontinue avelumab therapy per protocol 1.0 to 2.0 mg/kg/day methylprednisolone IV or equivalent Add prophylactic antibiotics for opportunistic infections Consider lower endoscopy	If improves: Continue steroids until Grade 1, then taper over at least 1 month If persists > 3 to 5 days, or recurs after improvement: Add infliximab 5 mg/kg (if no contraindication), Note: Infliximab should not be used in cases of perforation or sepsis

Dermatological irAEs		
Grade of Rash (NCI-CTCAE v4)	Management	Follow-up
Grade 1 to 2 Covering ≤ 30% body surface area	Symptomatic therapy (for example, antihistamines, topical steroids) Continue avelumab therapy	If persists > 1 to 2 weeks or recurs: Consider skin biopsy Delay avelumab therapy Consider 0.5 to 1.0 mg/kg/day methylprednisolone IV or oral equivalent. Once improving, taper steroids over at least 1 month, consider prophylactic antibiotics for opportunistic infections, and resume avelumab therapy If worsens: Treat as Grade 3 to 4
Grade 3 to 4 Covering > 30% body surface area; life threatening consequences	Delay or discontinue avelumab therapy Consider skin biopsy Dermatology consult 1.0 to 2.0 mg/kg/day methylprednisolone IV or IV equivalent	If improves to Grade 1: Taper steroids over at least 1 month and add prophylactic antibiotics for opportunistic infections Resume avelumab therapy
Pulmonary irAEs		
Grade of Pneumonitis (NCI-CTCAE v4)	Management	Follow-up
Grade 1 Radiographic changes only	Consider delay of avelumab therapy Monitor for symptoms every 2 to 3 days Consider Pulmonary and Infectious Disease consults	Re-image at least every 3 weeks If worsens: Treat as Grade 2 or Grade 3 to 4
Grade 2 Mild to moderate new symptoms	Delay avelumab therapy Pulmonary and Infectious Disease consults Monitor symptoms daily, consider hospitalization 1.0 mg/kg/day methylprednisolone IV or oral equivalent Consider bronchoscopy, lung biopsy	Re-image every 1 to 3 days If improves: When symptoms return to near Baseline, taper steroids over at least 1 month and then resume avelumab therapy and consider prophylactic antibiotics If not improving after 2 weeks or worsening: Treat as Grade 3 to 4

Grade 3 to 4 Severe new symptoms; New / worsening hypoxia; life-threatening
	
Discontinue avelumab therapy Hospitalize Pulmonary and Infectious Disease consults 2 to 4 mg/kg/day methylprednisolone IV or IV equivalent Add prophylactic antibiotics for opportunistic infections Consider bronchoscopy, lung biopsy
	
If improves to Baseline: Taper steroids over at least 6 weeks If not improving after 48 hours or worsening: Add additional immunosuppression (for example, infliximab, cyclophosphamide, IV immunoglobulin, or mycophenolate mofetil)

Hepatic irAEs
		

Grade of Liver Test Elevation (NCI-CTCAE v4)
	
Management
	
Follow-up

Grade 1 Grade 1 AST or ALT > ULN to 3.0 x ULN and / or total bilirubin > ULN to 1.5 x ULN
	
Continue avelumab therapy
	
Continue liver function monitoring If worsens: Treat as Grade 2 or 3 to 4

Grade 2 AST or ALT > 3.0 to ≤ 5 x ULN and / or total bilirubin > 1.5 to ≤ 3 x ULN
	
Delay avelumab therapy Increase frequency of monitoring to every 3 days
	
If returns to Baseline: Resume routine monitoring, resume avelumab therapy If elevations persist > 5 to 7 days or worsen: 0.5 to 1 mg/kg/day methylprednisolone or oral equivalent and when LFT returns to Grade 1 or Baseline, taper steroids over at least 1 month, consider prophylactic antibiotics for opportunistic infections, and resume avelumab therapy


Grade 3 to 4 AST or ALT > 5 x ULN and / or total bilirubin > 3 x ULN
	
Discontinue avelumab therapy Increase frequency of monitoring to every 1 to 2 days 1.0 to 2.0 mg/kg/day methylprednisolone IV or IV equivalent Add prophylactic antibiotics for opportunistic infections Consult gastroenterologist
	
If returns to Grade 2: Taper steroids over at least 1 month If does not improve in > 3 to 5 days, worsens or rebounds: Add mycophenolate mofetil 1 gram (g) twice daily If no response within an additional 3 to 5 days, consider other immunosuppressants per local guidelines

	Consider obtaining MRI/CT scan of liver and liver biopsy if clinically warranted	
Endocrine irAEs		
Endocrine Disorder	Management	Follow-up
Asymptomatic TSH abnormality	Continue avelumab therapy If TSH < 0.5 x LLN, or TSH > 2 x ULN, or consistently out of range in 2 subsequent measurements: include T4 at subsequent cycles as clinically indicated; consider endocrinology consult	
Symptomatic endocrinopathies	Evaluate endocrine function Consider pituitary scan Symptomatic with abnormal lab / pituitary scan: Delay avelumab therapy 1 to 2 mg/kg/day methylprednisolone IV or by mouth equivalent Initiate appropriate hormone therapy No abnormal lab / pituitary MRI scan but symptoms persist: Repeat labs in 1 to 3 weeks / MRI in 1 month	If improves (with or without hormone replacement): Taper steroids over at least 1 month and consider prophylactic antibiotics for opportunistic infections Resume avelumab therapy Subjects with adrenal insufficiency may need to continue steroids with mineralocorticoid component
Suspicion of adrenal crisis (for example, severe dehydration, hypotension, shock out of proportion to current illness)	Delay or discontinue avelumab therapy Rule out sepsis Stress dose of IV steroids with mineralocorticoid activity IV fluids Consult endocrinologist If adrenal crisis ruled out, then treat as above for symptomatic endocrinopathies	

ADL = activities of daily living; ALT = alanine aminotransferase; AST = aspartate aminotransferase; CT = computed tomography; irAE = immune-related adverse event; IV=intravenous; LFT = liver function test; LLN = lower limit of normal; MRI = magnetic resonance imaging; NCI-CTCAE = National Cancer Institute-Common Terminology Criteria for Adverse Event; T4 = free thyroxine; TSH = thyroid-stimulating hormone; ULN = upper limit of normal.

5.3.6 Intra-patient dose re-escalation for patients who have had dose-reductions due to hematological or non-hematological toxicity:

Once the MTD/RP2D has been established in the lead-in, the avelumab dose

will not be reduced or escalated during the phase II portion. Intra-patient dose re-escalation of 5-azacytidine (in accordance with the dosing schema in table 1) will be permitted provided:

- Patient has completed ≥ 1 cycle at their current dose level
- Patient has not experienced any grade 3 or higher non-hematologic drug-related toxicity, and
- Patient has not experienced drug-related hematologic DLT, and
- At least 6 patients have been treated at the next higher dose level and followed for at least 28 days without experiencing DLT.
- The dose may be escalated by one dose level per cycle (per table 1) provided such dose level does not exceed the established MTD/RP2D, whichever is lower. Dose level 0 is the maximum dose to be evaluated on this study. No dose escalation beyond dose level 0 will be permitted at any time on this study.

5.3.7 Modifications of dose schedules other than the above will be allowed within the following guidelines:

5.3.7.1 Dose adjustments by more than 1 dose level at a time (e.g., from 5-azacytidine 75 mg/m² to 25 mg/m²) can be considered when judged in the best interest of the patient (e.g. severe myelosuppression) when toxicity has resolved. The reason for this reduction will be discussed with the PI or Co-PI and documented in the medical record.

5.3.7.2 A patient who has had a dose reduction because of any of the reasons mentioned above may have their dose escalated provided the patient has remained free of toxicity requiring dose adjustments as defined above for at least 1 month. Escalation will be made by 1 dose-level increment only, and not more frequent than every month.

5.3.7.3 Treatment interruptions and dose modifications other than the ones mentioned above can be considered after discussion with the PI and proper documentation of the rationale. Dose adjustment/delay of only one of the agents is permissible if the toxicity is most likely judged to be related to one of the agents by the investigator (e.g., in patients with autoimmune thyroiditis or autoimmune hepatitis this would be likely secondary to avelumab, in patients with cytopenia's this would be likely secondary to 5-azacytidine).

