Investigators should, whenever possible, determine which medication is causing the toxicity and interrupt or dose reduce 5-azacytidine and/or interrupt avelumab, as applicable. No dose reductions (only interruptions) are permitted for avelumab in the phase II portion after RP2D has been established.

Dose reductions of azacytidine [to be implemented in the phase II portion of the study](#) will be as follows: dose level -1 of azacytidine: 50 mg/m², dose level -2: 37.5 mg/m², dose level -3: 25 mg/m².

Table 2 Dose adjustments of azacytidine for non-hematologic drug-related AEs, clinically significant in the opinion of the investigator

Grade	Occurrence	Dose modification
1 or 2	Any time	No dose reduction
3 or 4 (Persistent grade 2: Consider similar dose adjustments if persistent and not responding to optimal management in the opinion of PI and treating physician)	1st and 2nd time	Hold 5-azacytidine. Resume 5-azacytidine at prior dose if recovery to \leq Grade 1 occurs within 14 days. If toxicity persists for 15-28 days, hold therapy and resume 5-azacytidine at prior dose if recovery to \leq Grade 1 OR resume 5-azacytidine at ONE dose level below current dose if recovery to \leq Grade 2. Dose re-escalation to prior dose of 5-azacytidine is permitted in accordance with the dose-escalation guidelines in section 5.3.6.
	3 rd and 4th time	Hold 5-azacytidine. Follow until toxicity \leq Grade 2. Resume 5-azacytidine at ONE dose level below current dose. Dose re-escalation of 5-azacytidine to prior dose is permitted in accordance with the dose-escalation guidelines in section 5.3.6..
	5th time	Discontinue therapy

5.3.3 Avelumab dose delay/interruption for immune-oncology drug-related AEs, clinically significant in the opinion of the investigator

Avelumab administration should be delayed for the following drug-related AEs, clinically significant in the opinion of the investigator:

- Any Grade \geq 2 non-skin AE, except that
 - Grade 2 fatigue or laboratory abnormalities do not require delay, however
 - Patients with ALT or AST > 3 and up to 5 x ULN or total bilirubin greater > 2.0 mg/dL and up to 3 x ULN or creatinine > 2.0 mg/dL and up to 3 x ULN should have avelumab treatment withheld.

Avelumab administration should be delayed for the following drug-related AEs, clinically significant in the opinion of the investigator:

- Any Grade 3 skin AE, or Grade 3 laboratory abnormality, with the following exceptions:

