 - Grade 3 lymphopenia or leukopenia does not require dose delay.
 - However, patients with ALT or AST > 5 x ULN or total bilirubin greater > 3 x ULN or creatinine > 3 x ULN should have avelumab treatment interrupted.
- Any AE, laboratory abnormality, or intercurrent illness, which in the judgment of the investigator, warrants delaying the dose of study medication.
- Avelumab dose reductions are not permitted in this study (only dose delays when indicated).

Subjects may resume treatment with study drug when the drug-related AE(s) resolve to Grade ≤ 1 or baseline value, with the following exceptions:

- Subjects may resume treatment in the presence of Grade 2 fatigue
- Subjects who have not experienced a Grade 3 drug-related skin AE may resume treatment in the presence of Grade 2 skin toxicity
- Drug-related pulmonary toxicity, diarrhea, or colitis, must have resolved to baseline or at least \leq grade 1 before treatment is resumed
- Drug-related endocrinopathies adequately controlled may resume treatment

If the criteria to resume treatment are met, the subject should restart treatment at the next scheduled time point per protocol. However, if the treatment is delayed past the next scheduled time point per protocol, the next scheduled time point will be delayed until dosing resumes. Patients who receive combination therapy in whom continuation of 5-azacytidine is considered to be inadequate, or inappropriate (e.g., because of pancytopenia) can discontinue 5-azacytidine and continue with avelumab only.

If treatment is delayed > 8 weeks, the subject must be permanently discontinued from study therapy, except as specified in discontinuation section.

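### Sections 5.3.3, 5.3.4 and Table 3 give incompatible avelumab instructions for the same drug-related Grade 3 event, and nothing says which one governs

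*Combined protocol and SAP*

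**What the plan says.** Three places in the protocol govern what happens to avelumab after a Grade 3 event.

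- **Section 5.3.3 (delay/interruption).** The lead-in is "Avelumab administration should be delayed for the following drug-related AEs, clinically significant in the opinion of the investigator". The triggers are non-skin events of Grade 2 or above, with some exceptions, and "Any Grade 3 skin AE, or Grade 3 laboratory abnormality, with the following exceptions". Under those exceptions, AST or ALT above 5 x ULN, bilirubin above 3 x ULN and "creatinine > 3 x ULN should have avelumab treatment interrupted". On resumption: "Subjects may resume treatment with study drug when the drug-related AE(s) resolve to Grade" 1 or lower, or to baseline, with listed exceptions. A subject who meets the criteria is then to restart at the next scheduled dosing time.
- **Section 5.3.4 (discontinuation).** The lead-in is "The following ADRs require permanent treatment discontinuation of avelumab". For Grade 3 the rule is "Any Grade 3 AEs require treatment discontinuation with avelumab", subject to five exceptions. These include tumor flare (which covers rash at tumor sites), brief local reactions, and single laboratory values judged unlikely to be related to study treatment. Liver test increases of Grade 3 or higher are removed from the laboratory exception. Grade 4 events also require discontinuation, apart from certain isolated laboratory values judged unlikely to be related.
- **Table 3 (section 5.3.5).** For Grade 3 to 4 rash the management column says "Delay or discontinue avelumab therapy", and the follow-up column says to resume after improvement to Grade 1. For Grade 3 to 4 diarrhea/colitis, pneumonitis and liver test elevation, the instruction is to discontinue.

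**The concern.** These are the main rules for withholding and stopping the investigational drug. A reader who opens 5.3.3 holds the drug and restarts it after recovery. A reader who opens 5.3.4 stops it for good. What is at stake is patient safety, since rechallenge after a Grade 3 event would depend on which page was consulted, and consistent conduct of the trial. Section 9.3 lists noncompliance with discontinuation criteria as a class of protocol violation or deviation. Staff cannot be held to that standard when following one section breaches another.

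**Working it through.** No formula applies and the plan states no figure on this point. The check takes one drug-related, clinically significant event at a time, outside the 5.3.4 exceptions, and reads off each instruction.

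| Event | 5.3.3 | 5.3.4 | Table 3 |
|---|---|---|---|
| Grade 3 rash, not tumor flare or a transient local reaction | Delay, then resume | Permanent discontinuation | Delay or discontinue, then resume |
| Grade 4 rash | Not named | Permanent discontinuation | Same row as Grade 3: delay or discontinue, then resume |
| AST/ALT above 5 x ULN, or bilirubin above 3 x ULN | Interrupt; resumption criteria given | Permanent discontinuation (liver tests taken out of the laboratory exception) | Discontinue |
| Grade 3 diarrhea/colitis | Delay; specific resumption criterion | Permanent discontinuation | Discontinue |
| Grade 3 pneumonitis | Delay; specific resumption criterion for pulmonary toxicity | Permanent discontinuation | Discontinue |
| Drug-related creatinine above 3 x ULN, Grade 3 or higher | Interrupt; resumption criteria given | Permanent discontinuation | No renal row found; nothing rests on this |

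Three further checks look for something that would remove the conflict.

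1. **Scope.** Section 5.3.3 is limited to drug-related, clinically significant events. Section 5.3.4 opens with adverse drug reactions and then speaks of any Grade 3 event. A drug-related, clinically significant Grade 3 event falls under both.
2. **Resumption after Grade 3 skin events.** Section 5.3.3 adds: "Subjects who have not experienced a Grade 3 drug-related skin AE may resume treatment in the presence of Grade 2 skin toxicity". Withholding that concession from patients who have had a Grade 3 skin event makes sense only if those patients can also resume, under the stricter general rule. Section 5.3.4 would already have stopped them permanently.
3. **Precedence.** The only link from 5.3.3 to the discontinuation section concerns delays longer than 8 weeks. Section 5.3.5 describes Table 3 as guidance, which bears on the table's standing but does not rank 5.3.3 against 5.3.4.

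**The case against.** The best defence is that the sections work in sequence: 5.3.3 is the immediate hold and 5.3.4 the final decision. The word *may* in the 5.3.3 resumption rule would then leave 5.3.4 free to override it, with Table 3 as subordinate guidance. For the non-skin classes this reading is possible, because the Grade 2 or above trigger is broad and the resumption criteria could be meant for Grade 2 events. But the protocol does not say so, and 5.3.3 also directs that a subject who meets the criteria should restart. For rash the defence fails, because both 5.3.3 and Table 3 contemplate resumption after a Grade 3 event. Section 5.3.7.3 lets the principal investigator agree other modifications, but that discretion does not say which written rule is the default.

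Some stronger readings are tempting, and the documents do not support them.

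- *Every Grade 3 event has three competing instructions.* Only rash does. For liver tests, diarrhea/colitis and pneumonitis, Table 3 agrees with 5.3.4.
- *The 5.3.4 exceptions ignore skin altogether.* They cover tumor-flare rash and transient local reactions. Generalised drug-related rash is what they leave out.
- *About 12 Phase II patients are exposed (0.30 x 40 = 12).* The 30% in section 11.2 is the level above which drug-related Grade 3/4 toxicity of the combination is unacceptable. It includes 5-azacytidine toxicity and does not estimate these events. Nor is it a ceiling: Table 7 stops accrual at 17 of 35 only.
- *Toxicity monitoring is distorted.* The rule counts patients with a drug-related Grade 3/4 toxicity. A patient with such an event is already counted, whether avelumab is then delayed or stopped.
- *The ORR is biased because drop-outs count as failures.* The analysis plan refers to dropping out of the study. Stopping avelumab is not shown to be that: section 9.1.4 keeps patients who discontinue treatment on study for follow-up, and 5.3.7.3 permits adjusting or delaying one agent alone. Response is assessed within 3 months, and 5.4.2 asks for only one avelumab dose with a 7-day 5-azacytidine course. An effect on ORR is possible but not established.

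**Conclusion.** The contradiction holds on the text alone. It is three-way for Grade 3 rash outside the listed exceptions, and the same Table 3 row conflicts with 5.3.4 at Grade 4. For liver tests, diarrhea/colitis and pneumonitis, 5.3.3 stands against 5.3.4 and Table 3. For drug-related creatinine above 3 x ULN at Grade 3 or higher, 5.3.3 stands against 5.3.4. No passage settles 5.3.3 against 5.3.4. The size is therefore five event classes with conflicting instructions and an unknown number of patients. The conclusion assumes only that the event is drug-related, clinically significant and outside the 5.3.4 exceptions. It should be corrected on grounds of patient safety and consistent conduct. It does not rest on any effect on the stopping boundaries or the primary analysis.

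**What to change.** Reconcile 5.3.3, 5.3.4 and Table 3 so that each event class and grade carries one avelumab instruction, and state which section takes precedence if they still differ. In particular:

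- Separate Grade 3 from Grade 4 in the Table 3 rash row, or confirm in 5.3.4 that one instruction is meant for both.
- Say whether the 5.3.3 resumption criteria apply after Grade 3 events. If 5.3.3 is meant only as the immediate hold pending a decision under 5.3.4, write that down.
- Give liver tests and creatinine the same instruction wherever they appear.

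Which instruction is right for each class is for the sponsor and the medical monitor to decide. The cost is a wording amendment, with the approvals that section 12.0 requires, and notice to staff. Sample size, monitoring boundaries and analyses do not change.
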